Specific Aim 1: The primary objective is to investigate the effects of lofexidine in adults (N=25) undergoing opioid tapering. In this phase 4 clinical trial, an open label, variable dose design will be used to facilitate opioid tapering during a 15-day period. The primary outcome measure of this study is the number of patients who discontinue opioid use at day 15.

Specific Aim 2: Secondary aims include investigating the effects of lofexidine on the severity of OWS, pain intensity, negative affect, and opioid craving following completion of the 15-day study period. Secondary outcome measures will include the Clinical Opiate Withdrawal Scale, the Short Opiate Withdrawal Scale-Gossop, the numerical pain rating scale, Center for Epidemiologic Studies-Depression scale, the Pain Catastrophizing scale, and a composite scale of opioid craving.

Specific Aim 3: This exploratory aim will investigate the change in heat pain perception attributed to changes in opioid induced hyperalgesia. Prior to the opioid taper and on day 15, quantitative sensory testing will be conducted using the Computer Aided Sensory Evaluator IV (WR Electronics, Stillwater, MN).

B. PROCEDURES AND METHODS

B.1. Study Site

The study will be conducted at the medical (e.g., pain clinic, pain rehabilitation center) and surgical (e.g., orthopedic and spine surgery clinics) clinics at Mayo Clinic Rochester, MN. All patients will be recruited from the medical and surgical clinics at Mayo, and all assessments and follow-up will be conducted in the pain clinic and pain rehabilitation center.

B.2. Study Design

B.2.1. Study methodology

A prospective, open label, single center, variable dose design will be used to investigate the effects of lofexidine in adults undergoing a 15-day taper. The primary outcome will be the number of subjects who discontinue opioid use at day 15.

B.2.2. Opioid tapering

Following informed consent, the baseline opioid dose will be reduced 5% to 50% based on the physician investigators clinical discretion and patient acceptability of the dose reduction. The physician investigators will reassess each patient for further opioid dose reductions (5% to 50% allowed) in the pain clinic or pain rehabilitation center on study days 3, 6, and 9. On all other study days, patients will be contacted by telephone by study personnel to assess for OWS and adverse effects related to lofexidine use.

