Prior to initiating the opioid taper, the physician investigators will contact the physician or provider responsible for prescribing long-term opioid therapy. During the 15-day study period, the physician investigators will assume full prescribing authority, and patients and their established prescribers will be asked to halt the provision of all opioid prescriptions during the study period. Upon completion of the study, the physician investigators will contact the

established long-term prescriber to ensure continuity of care with the provision of ongoing prescriptions.

B.2.3. Variable lofexidine dosing

Upon initiation of the opioid taper, patients will receive oral lofexidine 0.54 mg 4 times daily (3 tablets of 0.18 mg 4 times daily) for a total daily dose of 2.16 mg. The variable dose design will allow the lofexidine dose to be increased up to 0.72 mg 4 times daily (4 tablets of 0.18 mg 4 times daily) by the physician investigators if OWS are elevated. The lofexidine dose may also be reduced by the physician investigators to 0.18 mg 4 times daily) to relieve adverse effects attributed to lofexidine.

On study days 10 through 15, equal quantities of the baseline lofexidine dose will be reduced, and lofexidine will be discontinued on day 15. All patients will be contacted within 24 hours of study completion to assess for any residual or late emerging adverse effects.

B.2.4. Heat pain perception

Prior to opioid tapering and on day 15, quantitative sensory testing will be conducted using the automated Computer Aided Sensory Evaluator IV (CASE IV; WR Medical Electronics, Stillwater, MN) system based on the method of levels. The CASE IV system delivers a series of short duration heat stimuli of variable magnitude interspersed with null stimuli in random order through a thermode with surface area of 10 cm². The validated HP test algorithm takes less than 5 minutes to complete. This protocol includes the standardized test procedures, stimulus waveform, null stimulus, and non-repeating stepping algorithm between the different levels of heat stimuli. The subject is masked to each level of stimulus delivered, including the null stimulus. Immediately after the stimulus is given, the subject then rates the stimulus intensity on an 11-point rating scale (0 denotes no pain, 10 denotes the most intense possible pain). The test is completed when either the maximum stimulus has been delivered, or when the subject grades the stimulus intensity ≥ 5.

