- 2. Medical or surgical conditions that could be adversely impacted by opioid tapering or use of lofexidine including, but not exclusively limited to, cardiac disease, inflammatory bowel disease, renal or hepatic impairment, vascular disease, and history of anaphylaxis. Patients may be excluded for other comorbid medical or surgical conditions based on the physician investigator's discretion.
- 3. History of schizophrenia or other chronic psychiatric disorder that could be adversely impacted by opioid tapering or use of lofexidine. Patients may be excluded for other comorbid mental health conditions based on the physician investigator's discretion.
- 4. Neurological condition that impair functioning in an ambulatory setting or could be adversely impacted by opioid tapering or use of lofexidine including, but not exclusively limited to, Parkinson's disease, amyotrophic lateral sclerosis, or a dementing illness. Patients may be excluded for other neurological conditions based on the physician investigator's discretion.
- 5. Active substance abuse disorder.
- 6. Inability to function in an ambulatory care setting due to severe deconditioning requiring use of supportive gait aids including a cane or walker. Patients may be excluded for other functional problems based on the physician investigator's discretion.
- 7. History of adverse effects attributed to opioid tapering or lofexidine use.
- 8. Use of medications from drug classes known to have adverse interactions with lofexidine including, but not exclusively limited to, beta-blockers, calcium channel blockers, alpha 1 and 2 receptor antagonists, tricyclic antidepressants, benzodiazepines, and selective serotonin reuptake inhibitors. Patients may be excluded for use of other medications based on the physician investigator's and research pharmacy's discretion.

B.4. Sample Size

The primary aim of this study is to assess the effects of lofexidine on opioid tapering in adults. The purpose of this open label study is to decide whether additional studies using an experimental design are warranted, and to provide preliminary data for designing a larger efficacy trial. The primary outcome will be the number of subjects who discontinue opioids at day 15. We anticipate opioid discontinuation will be observed in 50% to 70% of patients. Thus, a sample-size of N=25 will be sufficient to assess whether additional studies of lofexidine in this patient population are warranted.

B.5. Data Collection and Assessments

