The severity of opioid withdrawal symptoms will be assessed using two measures. First, the Clinical Opiate Withdrawal Scale (COWS) is an observer-rated instrumaent. Total score range from 0 to 47. Scores ranging from 5-12 denote mild withdrawal symptoms, scores from 13-24 signify moderate withdrawal, scores from 25-36 indicate moderately severe symptoms, and scores greater than 36 indicate severe withdrawal symptoms. Second, the Short Opiate Withdrawal Scale-Gossop (SOWS-Gossop) is a subjective score provided by the subject. It includes 10 items assessed by the patient as none/not present (0 points), mild (1 point), moderate (2 points), or severe (3 points).

B.5.9. Lofexidine adverse effects

According to previous reports, common adverse effects associated with lofexidine include orthostatic hypotension, hypotension, bradycardia, insomnia, somnolence, sedation, dry mouth, syncope, and tinnitus. Management of adverse effects is described in the Human Subjects section.

B.5.10. Urine toxicology screening

The opioid status of all patients will be biochemically verified with a confirmed urine toxicology screen prior to the opioid taper and at day 15.

B.5.11. Timeline of patient assessments

Screening visit (at least (7) days before baseline assessment)

Screen for inclusion and exclusion criteria.

Obtain informed consent.

Obtain urine toxicology screen and ECG.

Day 1 (baseline)

Informed consent reviewed and documented.

Physical examination performed, vital signs documented.

Determine opioid dose reduction.

Start lofexidine.

Obtain baseline assessments.

Day 3+3 days (pain clinic follow-up with physician investigator)

Physical examination performed, vital signs documented.

Determine opioid dose reduction.

Assess for opioid withdrawal and lofexidine adverse effects.

Lofexidine dose adjustment if indicated.

Day 6 +3 days(pain clinic follow-up with physician investigator)

Physical examination performed, vital signs documented.

Determine opioid dose reduction.

Assess for opioid withdrawal and lofexidine adverse effects.

Lofexidine dose adjustment if indicated.

Day 9 + 3 days (pain clinic follow-up with physician investigator)

Physical examination performed, vital signs documented.

Determine opioid dose reduction.

Assess for opioid withdrawal and lofexidine adverse effects.

Lofexidine dose reduction initiated.

Day 12 to 15 (pain clinic follow-up with physician investigator)

Physical examination performed, vital signs documented.

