Assess for opioid withdrawal and lofexidine adverse effects.

Determine opioid new baseline dose.

Lofexidine discontinued.

Obtain day 15 assessments.

Days 1-15 (telephone assessment)

Daily telephone call to assess for opioid withdrawal, pain, and lofexidine adverse effects.

B.6. Data Handling

The working database will be maintained on a secure institutional server. All computer files and systems will be password protected and accessible by authorized study personnel only. Data entry will be performed by the research coordinator.

B.7. Data Analysis

Demographics (e.g., age, sex, marital status, educational status, employment status), and clinical characteristics (e.g., pain duration, depression, pain intensity) will be summarized. Mean and standard deviation will be calculated for continuous variables, and count and proportion will be calculated for categorical variables. The primary outcome measure will be the number of patients who discontinue opioid use at day 15. In the analysis of secondary aims, nonparametric paired tests will be used to assess for differences in pre- and post-taper scores of opioid withdrawal, pain intensity, negative affect, and heat pain perception. The frequency of all lofexidine adverse effects will be documented. Perioperative opioid use and pain scores will be summarized.

B.8. Strengths and Limitations

At the conclusion of this project, we will have investigated the effects of lofexidine in adults undergoing opioid tapering. These data will be critical to the design of a future efficacy trial of lofexidine in this patient population.

All study participants will be recruited from the medical and surgical clinics at a tertiary referral medical center. As a result, the study findings may not be applicable to all adults undergoing elective lumbar spine surgery.

References

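### The patient-reported effects listed in B.5.9 have no specified pre-dose record, so the adverse-effect count cannot reliably separate new symptoms from those already present

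*Combined protocol and SAP*

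**What the plan says.** Section B.5.9 names nine effects: "According to previous reports, common adverse effects associated with lofexidine include orthostatic hypotension, hypotension, bradycardia, insomnia, somnolence, sedation, dry mouth, syncope, and tinnitus". Hypotension, orthostatic hypotension and bradycardia are measured signs, and syncope is an event. The other five rest mainly on what the patient reports.

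The schedule in B.5.11 runs as follows.

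- **Screening:** eligibility, consent, and "Obtain urine toxicology screen and ECG". No symptom inquiry is named.
- **Day 1:** consent review, physical examination with vital signs, the opioid reduction decision, the start of lofexidine, and then a line for baseline assessments whose contents are not itemised.
- **Day 3 and later visits:** adverse effects are assessed, for the first time at a clinic visit.
- **Days 1 to 15:** "Daily telephone call to assess for opioid withdrawal, pain, and lofexidine adverse effects".

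The baseline characteristics in B.5.1 include no symptoms from the B.5.9 list. On analysis, B.7 says only: "The frequency of all lofexidine adverse effects will be documented". It gives no definition of a treatment-emergent effect, no baseline comparison and no attribution criterion. Section B.2.1 describes the design: "A prospective, open label, single center, variable dose design will be used". There is no comparator arm.

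**The concern.** Without a control arm, each patient's own pre-dose state is the only reference inside the study. B.7 uses that logic for withdrawal, pain intensity, negative affect and heat pain, all of which get paired pre-taper and post-taper comparisons. Adverse effects, the only safety summary in B.7, do not.

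Under B.3.1 every patient has had pain for at least three months and takes at least 20 mg/day of morphine equivalent. Poor sleep, sedation or dry mouth may well be present before the first lofexidine tablet. A question first put to patients already on lofexidine shows how common a symptom is, not whether it is new.

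B.4 says the study is meant to inform the decision on further studies and to supply preliminary data for a larger trial, so its tolerability figures may be carried forward. Pre-dose status cannot be reliably recovered once dosing has begun.

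**Working it through.** **Plan's own figure.** The documents state no adverse-effect rate, baseline symptom prevalence or precision target, so there is no figure to reproduce. The one input taken from the plan is N = 25 (B.4).

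**Which terms have a pre-dose reference.**

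| B.5.9 term | Pre-dose record named in the plan |
|---|---|
| Hypotension, bradycardia | Yes: Day 1 vital signs and screening ECG |
| Orthostatic hypotension | Only if postural readings are taken, which is not stated |
| Syncope | An event; no history item is named |
| Insomnia, somnolence, sedation, dry mouth, tinnitus | None named |

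**Size, on assumed inputs.** Let b be the proportion with a given symptom before dosing, and i the risk of new onset among patients without it. Both are assumptions. Assume also that every pre-existing symptom persists and is counted. Then:

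- crude on-treatment frequency = b + (1 − b) × i
- newly affected, as a share of all patients = (1 − b) × i
- excess of the first over the second = b

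With i = 0.20 and N = 25:

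| b | Crude frequency | Crude count | Newly affected | New count |
|---|---|---|---|---|
| 0.10 | 0.10 + 0.90 × 0.20 = 28% | 7 | 18% | 4.5 |
| 0.20 | 0.20 + 0.80 × 0.20 = 36% | 9 | 16% | 4 |
| 0.30 | 0.30 + 0.70 × 0.20 = 44% | 11 | 14% | 3.5 |
| 0.40 | 0.40 + 0.60 × 0.20 = 52% | 13 | 12% | 3 |

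Both columns use all 25 patients as denominator. The excess runs from 7 − 4.5 = 2.5 patients to 13 − 3 = 10 patients. As b rises, the crude figure goes up while the number newly affected goes down.

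**Whether the problem is likely to arise.** The chance that at least one of 25 patients already has a given symptom is 1 − (1 − b)^25. This is 72% at b = 0.05 and 93% at b = 0.10.

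**The case against.** The strongest case on the other side is that the plan is silent on this point, not shown to be defective. Several parts of that case stand, and they limit what can be concluded.

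- **Baseline symptoms may be partly captured.** The Day 1 baseline assessments are not itemised, and B.7 requires pre-taper withdrawal scores, one of them from a ten-item patient-rated scale (B.5.8). The items are not listed, so overlap with B.5.9 can be neither confirmed nor excluded. A reader might infer that no symptom data exist before dosing, or that the baseline assessments follow the first dose because they are printed after it. The documents support neither: printed order need not be order of conduct. What can be said is that no pre-dose inquiry about these five symptoms is specified, and that B.7 does not link withdrawal scores to the adverse-effect count.
- **Mixing is a likely consequence, not a stated rule.** B.7 counts effects of lofexidine, and B.2.3 allows dose reduction "to relieve adverse effects attributed to lofexidine". Both imply some attribution by the investigator, so not every symptom present need be counted. But no criterion is given, and without a pre-dose record such judgements would lean on recall in an open-label study.
- **Effect on dosing.** A reader might also infer that pre-existing symptoms will prompt lofexidine reductions. Nothing in the documents shows this. Physician investigators make those decisions, with an examination at every visit.
- **A cited section is missing from the available text.** B.5.9 refers to a Human Subjects section for management of adverse effects. It may define them, so its silence cannot be assumed.
- **Importance.** Adverse-effect frequency is descriptive, the primary outcome is opioid discontinuation, and the background section cites a placebo-controlled trial of more than 600 patients. Tolerability planning therefore need not rest on these 25 alone.

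These points narrow the concern but do not remove it. Followed as written, the plan does not ensure the data needed to tell old symptoms from new.

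**Conclusion.** The point holds for insomnia, somnolence, sedation, dry mouth and tinnitus. No pre-dose inquiry about them is specified, and the planned analysis makes no reference to the pre-dose state, so their reported frequency cannot reliably separate pre-existing from new symptoms. It does not extend to the whole B.5.9 list, since hypotension and bradycardia have pre-dose values. The primary outcome is untouched.

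The actual bias cannot be derived from the documents. The illustrated excess of 2.5 to 10 patients is an upper bound for the assumed values: the opioid dose is falling, so some old symptoms may resolve, and investigators may discount others. A reader might set the crude 28% to 52% against the assumed 20% and call the gap the bias. That would compare a proportion of all 25 patients with a risk among symptom-free patients only; the like-for-like figure is 18% to 12%.

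**What to change.** In B.5.11, add to Day 1, before the first lofexidine dose, a record of the presence and severity of each patient-reported B.5.9 symptom. Use the same checklist in the daily calls and at the visits.

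In B.7, report for each symptom the number and proportion of patients in whom it is new or worse than on Day 1. Show the pre-dose prevalence and the crude on-treatment frequency beside it. The new-or-worse count will also include worsened symptoms, which the illustration above leaves out.

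The cost is a slightly longer Day 1 visit and about one sentence in each section. The change will not separate effects of lofexidine from effects of the opioid taper, because both begin together; the report should say so.

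### Safety counts in B.7 and the visit schedule cover only lofexidine-attributed effects, so the reported frequency rests on an unblinded judgement of cause that the design makes hard to reach

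*Combined protocol and SAP*

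**What the plan says.** B.7 (Data Analysis) plans one safety summary: "The frequency of all lofexidine adverse effects will be documented".

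Collection is worded in a similar way.

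- B.2.2, for days without a clinic visit: "patients will be contacted by telephone by study personnel to assess for OWS and adverse effects related to lofexidine use".
- B.5.11, for the visits on days 3, 6, 9 and 12 to 15: "Assess for opioid withdrawal and lofexidine adverse effects".
- B.5.11, for days 1 to 15: "Daily telephone call to assess for opioid withdrawal, pain, and lofexidine adverse effects".

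B.5.9 carries the same term as its heading and states that "common adverse effects associated with lofexidine include orthostatic hypotension, hypotension, bradycardia, insomnia, somnolence, sedation, dry mouth, syncope, and tinnitus". It does not say whether the count is confined to that list.

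The design, from B.2.1: "A prospective, open label, single center, variable dose design will be used to investigate the effects of lofexidine in adults undergoing a 15-day taper". No control arm is described.

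Other parts of the plan reach further. Visits include an examination and vital signs. B.5.8 measures withdrawal with COWS and SOWS-Gossop. The contact within 24 hours of completion (B.2.3) asks about remaining or delayed adverse effects without limiting them by cause. B.5.9 also refers the management of adverse effects to a Human Subjects section, which is not in the text available for this review.

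**The concern.** Counting only effects ascribed to the drug requires someone to decide the cause before an event is counted. In this design that decision is unusually hard. Lofexidine begins when the first opioid reduction is made (B.2.3; B.5.11, day 1), everyone knows the treatment, and there is no comparison group to show how often the same symptom arises from tapering alone. Insomnia, which B.5.9 lists, shows the difficulty. The plan gives no causality rule.

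According to B.4, the study is to inform whether further trials are warranted and to supply preliminary data for a larger one. A frequency already filtered by attribution is a weak input to that planning, because the all-cause frequency cannot be recovered from it.

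**Working it through.** The plan states no adverse event rate, so there is no figure to reproduce. The check has two parts.

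**Where an event goes under the plan as written**

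| How the event is judged | What B.7 does with it |
|---|---|
| Due to lofexidine | Counted |
| Due to withdrawal and still present at day 15 | May raise the post-taper COWS or SOWS-Gossop score; not counted as an event |
| Due to withdrawal, resolved before day 15 | No count; absent from the pre/post comparison |
| Due to neither (for example, a fall put down to another cause) | No count |

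Withdrawal is also assessed at the intermediate visits and calls, but B.7 tests only pre- against post-taper scores. Vital signs are recorded at visits, but B.7 plans no summary of them. The 24-hour contact collects without a filter, yet the B.7 sentence would still filter what is reported from it.

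**How much attribution can move a rate**

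Inputs: n = 25 (Specific Aim 1; B.4). Event rates and attributed shares are not in the documents, so every value below is assumed for illustration. The exact (Clopper-Pearson) 95% limits for x of n are the 0.025 quantile of Beta(x, n − x + 1) and the 0.975 quantile of Beta(x + 1, n − x).

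1. One patient is 1/25 = 4 percentage points. This applies to a patient whose only occurrence of the event is reclassified; a patient with another counted occurrence stays in the numerator.
2. Loss from the count: 5 patients have the event from any cause, 5/25 = 20% (6.8% to 40.7%). If 2 are called withdrawal, the report shows 3/25 = 12% (2.5% to 31.2%), a shift of 2 × 4 = 8 points.
3. The opposite error: 3 patients have a drug-caused event (12%) and 2 more have a withdrawal symptom that is called a lofexidine effect. The report shows 5/25 = 20%, which is 8 points above the drug-caused rate.
4. Range: expected reported rate = all-cause rate × share of affected patients attributed to lofexidine.

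| Assumed all-cause rate | 100% attributed | 75% | 50% | 25% |
|---|---|---|---|---|
| 20% | 20% | 15% | 10% | 5% |
| 40% | 40% | 30% | 20% | 10% |
| 60% | 60% | 45% | 30% | 15% |

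For the 20% row, and treating patients as independent, the chance that the event is missing from the report altogether is (1 − reported rate)^25: 0.4%, 1.7%, 7.2% and 27.7% from left to right.

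The filtered count can never exceed the all-cause count. As an estimate of drug-caused effects, however, steps 2 and 3 show that it can err either way. The exact limits reflect sampling error only and do not cover misattribution.

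**The case against.** The case against has four parts.

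- **Collection is wider than the B.7 sentence suggests.** Calls and visits also assess withdrawal, calls cover pain, visits include vital signs, and the final contact is unfiltered. This stands, and it narrows the gap to the last two rows of the first table. It does not close it, because B.7 assigns those events no count.
- **The term may simply be undefined.** It could mean the event types listed in B.5.9, counted whenever they occur; insomnia would then be counted without any judgement of cause. That reading is open, but it fits poorly with the B.2.2 wording, "to assess for OWS and adverse effects related to lofexidine use", and unlisted events would still go uncounted.
- **Safety is not among the three aims**, and B.4 ties the decision on further studies to opioid discontinuation at day 15. This stands: no primary or secondary result depends on the point.
- **The example splits are invented.** They are, and they show sensitivity only.

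A reader might also infer stronger claims that the documents do not support. One is that the study has no wider safety reporting anywhere; with the Human Subjects section unavailable, this cannot be established. A second is that the physicians who set the doses also decide what is counted. The attribution wording in B.2.3 concerns dose reduction, study personnel make the calls, and nobody is named as judging cause for the tabulation. A third is that the drug's adverse effects are most likely understated; withdrawal symptoms wrongly assigned to lofexidine would push the frequency up.

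**Conclusion.** The point holds for B.7, B.2.2 and B.5.11. As worded, the reported frequency can depend on an unblinded and unspecified judgement of cause, in a setting where drug and taper effects are confounded. Two kinds of event have no planned count in the available text: transient mid-taper events called withdrawal, and events put down to neither lofexidine nor withdrawal. The certain part of the size is 4 percentage points for each patient whose only occurrence is reclassified; how many patients that would be is unknown. The conclusion assumes that the term is applied as a causal filter, as B.2.2 suggests, and that the Human Subjects section does not already require an all-cause tabulation. It is worth correcting because the output is meant to inform later trials and a simple, better rule is available.

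**What to change.** In B.2.2 and B.5.11, ask about and record all adverse and serious adverse events from the first lofexidine dose to the post-study contact, whatever the suspected cause. In B.7, report for each event the number of patients affected over the number treated (n/N). Show the subset judged lofexidine-related in a separate column, and state who makes that judgement and by what rule. An exact 95% interval for each rate is optional. If the Human Subjects section already defines adverse event recording, B.7 should refer to it and use the same terms.

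The cost is slightly more recording on contacts that are already scheduled, one more table column, and a headline rate that may look less favourable. The collection wording should change first, since events not recorded at the time may not be recoverable at analysis.
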